### 3.3.12.5 Aim 4 (To evaluate the explanatory value of changes in alcohol craving, self-efficacy, motivation, and other psychological domains in accounting for the observed experimental effect of psilocybin relative to diphenhydramine control)

#### 3.3.12.5.1 Measures

For craving, the primary measure is the total score from The Penn Alcohol Craving Scale [148]; for self-efficacy, Abstinence Confidence from the Alcohol Abstinence Self-efficacy Scale [143]); and for motivation the "readiness" score from the Readiness Rulers [142]. Additional secondary measures are defined for depression (Hamilton Depression Scale score [152]) and anxiety (Hamilton Anxiety Scale score). Drinking outcomes will be those specified for Specific Aim 2.

#### 3.3.12.5.2 Method

Statistical procedures described for Aim 3 will be used to determine if the proposed mediators account for the effectiveness of the psilocybin administration. Changes in proposed primary and secondary mediators will be assessed at weeks 5 and 9 (1 week following drug administration) and drinking outcome (PHDD) will be assessed at weeks 8 and 12 (4 weeks post drug administration). No protection for inflated Type I error will be applied to the testing of the three primary mediators, i.e., Penn Alcohol Craving Scale, and Abstinence Self-efficacy from the AASE, and Readiness from the Readiness Rulers. Performance site and the site by treatment group interaction terms will not be entered into the model.

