### 3.3.3.2 Pilot Study Results

Figure 3 illustrates available pilot results by individual through week 8. Participants were 6 men and 4 women, mean age 40.1 (S.D. 10.3), who were concerned about their drinking but not interested in available treatment. Participants had been alcohol dependent for a mean of 15.1 years (S.D. 11.5) and ranged in severity from mild to severe dependence with a mean of 5.0 dependence criteria (S.D. 1.2).

Participants have tolerated psilocybin well in the pilot study. Transient mild headaches have been common during the 24 hours following psilocybin administration, as reported by Johnson et al. [109]. There have been no persisting adverse events that were considered related to the study treatments. Figure 3a shows mean scores on the Mystical Experience Questionnaire (MEQ) total score for the 10 participants receiving 0.3 mg/kg in the first session and 5 participants receiving 0.4 mg/kg in the second session, as well as scores reported at similar doses in normal volunteers by Griffiths et al. [110]. On average, acute effects are lower in magnitude than those seen at comparable doses in normal volunteers. Intensity of effects varied markedly from patient to patient, with MEQ scores ranging from .02 to .77 in the first session, and Hallucinogen Rating Scale (HRS) intensity scores ranging from 0 to 3.5. The mean score for the 0.4 mg/kg dose appears to be lower than that at 0.3 mg/kg. This is probably because the four participants with the strongest response in the first session did not receive 0.4 mg/kg in the second session.

Results (n=9) for the month before and the two months after the first psilocybin session are shown in Figures 3b-3d. Participants showed modest change in drinking behavior during the first month of psychosocial treatment. However, drinking days and heavy drinking days decreased significantly during the month following the first psilocybin session. Changes in drinking were accompanied by modest significant increases in self-efficacy (AASE confidence scale) following the psilocybin session. Importantly, the magnitude of the effects reported during the first psilocybin session (at week 4) is strongly correlated with changes in craving and self-efficacy in the week following the session, and with changes in drinking in the month following the session. In addition, changes in craving and self-efficacy at week 5 are correlated with changes in drinking during weeks 5-8 relative to weeks 1-4.

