**Figure 3a. MEQ Total Score****Figure 3b. Percent drinking days and Percent heavy drinking days****Figure 3c. Self-Efficacy (AASE Confidence)****Figure 3d. Correlations with intensity of 1st session**

Pearson's r (n = 9)	Change in PACS (wk 5-wk 4)	Change in AASE conf. (wk 5-wk 4)	Change in PDD (wk 8-wk 4)	Change in PHDD (wk 8-wk 4)
MEQ total (wk 4)	r = -.810 p = .008	r = .762 p = .017	r = -.884 p = .002	r = -.823 p = .006
HRS Intensity Scale (wk 4)	r = -.823 p = .006	r = .753 p = .019	r = -.834 p = .005	r = -.762 p = .017
HRS item 98 (wk 4)	r = -.862 p = .003	r = .803 p = .009	r = -.826 p = .006	r = -.711 p = .032
Change in PACS (wk 5-wk 4)			r = .762 p = .017	r = .726 p = .027
Change in AASE conf. (wk 5 - w 4)			r = -.611 p = .081	r = -.494 p = .177

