#### **3.3.12.3 Aim 2 (To evaluate the effect of psilocybin treatment on drinking outcomes for 32 weeks after the first administration, relative to diphenhydramine control)**

##### **3.3.12.3.1 Outcome measures**

The primary drinking outcome for hypothesis 2 is percent heavy drinking days during weeks 5-36 (the 32 weeks following the first drug administration session) as assessed by the Time-line Follow-back [100]. Other drinking variables will serve as secondary outcomes, including percent days abstinent, drinks per

drinking day, days to first drinking day, days to first heavy drinking day, and consequences of drinking (from the Short Inventory of Problems [101]).

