### 3.3.12.3.2 Method

For PHDD we will employ a MMRM including fixed, categorical effects of treatment, assessment, and site; site-by-treatment and treatment-by-assessment interactions; the continuous, a fixed covariate (week 1-4 PHDD); and using monthly values of PHDD (weeks 5-8, 9-12, 13-16, 17-20, 21-24, 25-28, 29-32, 32-36) as the dependent measure. Site and the site-by-treatment interaction will be removed from the final model if not significant at the  $p < 0.05$  level. Secondary drinking measures with a continuous scale of measurement, i.e., PDA and DPDD, will be tested in a similar fashion and for days to first drinking day and days to first heavy drinking day (5 or more standard drinks for a man, 4 or more standard drinks for a woman). Cox survival analysis will be used. Measures of effect size will be calculated for all planned between-group contrasts (Hedges  $d$ ) and the  $Q$  statistic will be calculated to assess the homogeneity of effect across the primary and secondary outcome measures of drinking.

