#### 3.3.12.4.2 Method

Tests of statistical mediation will use a product-of-coefficients approach with a bootstrapping procedure. This choice provides the most powerful test of mediation with smaller samples and does not assume normality in the distribution of ( $a'b'$ ) product terms (Preacher and Hayes, 2008; Hayes, 2009). HLM will be applied to identify the  $a$  and  $b$  parameter estimates for the between-group contrast (treatment assignment psilocybin versus control;  $df = 1$ ), and baseline values of the dependent variable will be entered in level 2.

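### Aim 4 leaves its PHDD window unstated; on the best-supported reading, a quarter of the outcome days come before the mediator is measured

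*Combined protocol and SAP*

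**What the plan says.** Aim 4 tests whether craving, self-efficacy and motivation carry the drug effect on drinking. On the mediators, section 3.3.12.5.2 states: "Changes in proposed primary and secondary mediators will be assessed at weeks 5 and 9 (1 week following drug administration". On the outcome it states: "drinking outcome (PHDD) will be assessed at weeks 8 and 12 (4 weeks post drug administration". It gives no start date for the PHDD window and no reference visit for the mediator change.

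Four other places bear on the window:

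- Section 3.3.12.5.1 (Aim 4 measures): "Drinking outcomes will be those specified for Specific Aim 2".
- Section 3.3.12.3.1 (Aim 2 outcome): "percent heavy drinking days during weeks 5-36 (the 32 weeks following the first drug administration session".
- Section 3.3.12.3.2 (Aim 2 model) uses "monthly values of PHDD (weeks 5-8, 9-12" and so on.
- Section 3.3.3.2 reports for the pilot that "changes in craving and self-efficacy at week 5 are correlated with changes in drinking during weeks 5-8 relative to weeks 1-4". Its correlation table labels that drinking change "Change in PHDD (wk 8-wk 4".

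Aim 4 borrows its statistical procedure from Aim 3, section 3.3.12.4.2: a product of coefficients with bootstrapping, in which "baseline values of the dependent variable will be entered in level 2".

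**The concern.** The causal model in section 3.1.8.1 and Hypothesis 4 in section 2 both run from the mediator to drinking. If PHDD covers weeks 5-8 and 9-12, the first week of each window has already happened when the mediator is measured. Someone who drank little that week may report less craving or more confidence as a result. The same week is then counted in the outcome.

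The b path (mediator to drinking) would pick up this drinking-to-mediator influence. Randomization protects the a path (treatment to mediator) but not the b path, and bootstrapping does not restore temporal order. The covariate in section 3.3.12.4.2 does not help: it is the baseline mediator in the a path and baseline drinking in the b path, and neither is drinking between the session and the mediator visit. At stake is whether a positive Aim 4 result can be read as support for Hypothesis 4.

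**Working it through.** **Calendar.** Sessions follow weeks 4 and 8 (section 1), that is days 28 and 56. Mediator visits come one week later (sections 3.3.12.5.2 and 3.3.15), nominally days 35 and 63. The plan's own lags reproduce: 5 − 4 = 9 − 8 = 1 week, and 8 − 4 = 12 − 8 = 4 weeks. Weeks 5-36 number 36 − 5 + 1 = 32, so week 5 is the first week after the session.

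- Session 1: window days 29-56; 35 − 28 = 7 days fall on or before the mediator visit.
- Session 2: window days 57-84; 63 − 56 = 7 days.
- Overlap: 7/28 = 25%.

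Table 1 (section 3.3.10) fits this reading. It schedules the Time-line Follow-back at weeks 4, 8 and 12 but not at weeks 5 or 9.

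**What the overlap does.** Suppose the mediator has no effect on later drinking and equals g × first-week drinking plus noise of SD √(1 − g²), with weekly drinking of SD 1. In the simplest case weeks are independent and treatment shifts each week by δ. Then a = gδ and, for the four-week mean, b = g/4. The share of the treatment effect wrongly credited to the mediator is ab/δ = g²/4:

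- g = 0.3: 0.09/4 = 2.25%
- g = 0.5: 0.25/4 = 6.25%

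The factor 1/4 is the 7/28 overlap. Starting the outcome in week 6 makes b zero in this case, but not when drinking persists from week to week. Across nine simulated correlation patterns the share was 2-4% and 6-11% with the full window, and 0-3% and 0-8% when lagged.

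**False mediation, one session.** Inputs:

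- N = 180 × 0.95 = 171 and f² = .065, both from section 3.3.12.7. Using that f² here is an assumption, because the plan gives it as the detectable effect over eight months.
- Assumed weekly drinking: a stable person component (SD 0, 0.5 or 0.7) plus autocorrelated variation (0, 0.3 or 0.5), total SD 1. Baseline is the mean of weeks 1-4.
- δ solved from f² = δ²p(1 − p)/Var(mean of weeks 5-8 given baseline), with p(1 − p) ≈ 0.25.

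Example with person SD 0.7 and no autocorrelation: the variance of the four-week mean is 0.49 + 0.51/4 = 0.6175. Given baseline it is 0.6175 − 0.49²/0.6175 = 0.2287. So δ = √(.065 × 0.2287/0.25) = 0.244. Over the nine patterns δ ran from 0.244 to 0.358 SD.

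Runs declaring mediation when there is none, full four-week window (not every set of runs covered all nine patterns):

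| Form of the mediator | g = 0.3 | g = 0.5 |
|---|---|---|
| Week-5 level | 2-7% | 11-21% |
| Simple change, week 5 minus week 4 | 0.5-4% | 4-16.5% |
| Week 5 adjusted for week 4 | 4-6% | 14-22% |

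At g = 0 the level mediator gave 0.0-0.2%, so without a reverse path there is no inflation.

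**Effect of the remedies (level mediator).**

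| Outcome | g = 0.3 | g = 0.5 |
|---|---|---|
| Weeks 6-8 | 0.2-2.1% | 0.4-11% |
| Weeks 6-8, week-5 PHDD as covariate | 0.2-0.6% | 0.2-1.0% |

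These rates use Monte Carlo intervals. The percentile bootstrap was checked in one pattern (person SD 0.5, autocorrelation 0.3). Lagging took the rate from 5.0% to 1.6% at g = 0.3 and from 16.8% to 6.6% at g = 0.5.

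**The case against.** The strongest reply has four parts.

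1. **The window is inferred.** Section 3.3.12.5.2 names only the assessment weeks, and section 3.3.12 refers to a separate SAP, not in the text reviewed, which could define another window. This stands. A reader might infer that the protocol prescribes the overlapping window; it does not. But every passage that bears on the question points that way, and an analyst working from the protocol would use it.

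2. **No reverse path is documented.** The mediator descriptions in section 3.3.10.7 do not present these scales as records of recent drinking, and no loading is given. This also stands. The case rests on temporal order, not on a demonstrated error rate.

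3. **The plan analyses changes in mediators.** Simple change scores lower the rates, as the table shows, so the size depends on a choice the plan leaves open. A reader might also infer rates of 20-36% at a loading of 0.5 by stacking both sessions. That range comes from one specification, with both changes taken from week 4 and a pooled regression. Using session-specific changes (week 5 minus 4, week 9 minus 8), stacked runs gave about 4-11%. The plan does not say how sessions are combined, so neither range can be attributed to it.

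4. **Lagging is partial and has a price.** It leaves bias when drinking persists, and it drops the first post-session week from the effect Aim 4 is meant to explain. Keeping four weeks as the main outcome with a lagged sensitivity analysis is a defensible alternative. Even so, lagging lowered false mediation in nearly all settings examined, and it restores the order that the hypothesis asserts.

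**Conclusion.** The point holds as a conditional ordering flaw in a secondary, mechanistic aim; its severity is minor to moderate. On the best-supported reading, 25% of each PHDD window precedes the nominal mediator visit and no planned covariate deals with this. Whether that produces false mediation depends on a reverse path the documents do not quantify. Under the stated assumptions the one-session rate is about 0.5-7% at a loading of 0.3, which is near or below nominal in most settings, and about 4-22% at 0.5. Loadings, correlations and the use of f² = .065 for a four-week outcome are all assumptions.

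It would go too far to infer that Aim 4 is invalid or that a positive result must be spurious. Nor does the point reach Aim 2: the primary analysis, sample size and stated power are unaffected.

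**What to change.** In section 3.3.12.5.2:

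- State the PHDD window, and the reference visit for the mediator change (week 4 for both sessions, or weeks 4 and 8).
- Start the Aim 4 PHDD outcome the day after the actual mediator visit, nominally weeks 6-8 and 10-12, and report the full four-week window alongside it.
- As a further sensitivity analysis, add week-5 or week-9 PHDD as a covariate. Note that this may remove true mediation, because first-week drinking may lie on the causal path, and do not make it a condition for claiming mediation.
- State that lagging reduces the bias but does not remove it when drinking persists.

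The cost is wording and a re-cut of daily Time-line Follow-back data already collected (section 3.3.10.4.1); no new visits are needed. The outcome shortens from 28 to about 21 days. In one-session runs with true mediation (assumed mediator shift 0.5 SD, total f² = .065), lagging cost about 0 points of power at a mediator-to-drinking slope of 0.3, 0-4 points at 0.2 and 6-11 at 0.1. Adding the first-week covariate raised the total loss to 0-8, 1-32 and 12-30 points, which is why it belongs in a sensitivity analysis.

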## 1. PROTOCOL ABSTRACT

Several lines of evidence suggest that classic hallucinogens such as psilocybin can facilitate behavior change in addictions such as alcohol dependence. The proposed investigation is a multi-site, double-blind active-controlled trial (n = 180, 90 per group) contrasting the acute and persisting effects of psilocybin to those of diphenhydramine in the context of outpatient alcoholism treatment. Two to four sites will participate. Aims of the study are 1) to characterize the acute effects of PO psilocybin 25 mg/70 kg, 30 mg/70 kg, and 40 mg/70 kg in alcohol dependent patients; 2) to evaluate the effect of psilocybin treatment on drinking outcomes for 32 weeks after the first administration, relative to diphenhydramine control; 3) to test whether or not characteristics of the drug administration session experiences mediate effects of psilocybin on short-term (1 week) persisting effects and post-session drinking behavior, 4) to evaluate the explanatory value of changes in alcohol craving, self-efficacy, motivation, and other psychological domains in accounting for the observed experimental effect of psilocybin relative to diphenhydramine control and 5) to evaluate pre-post changes in drinking in participants after they receive psilocybin in the third session.

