### 3.3.5 Randomization and Blinding

Randomization will be performed as close as possible to the first drug administration session (on the morning of the session if possible) in order to restrict the intent-to-treat sample to patients who actually receive study medication. The randomization will be stratified by site and will consist of balanced varied size blocks within strata to ensure relative equality of assignment across treatment groups. The block sizes will not be revealed to participating investigators and will be randomly selected from a small number of different block sizes to help reduce the likelihood of an investigator predicting the next treatment assignment. The study statistician will generate the randomization scheme for each site, and the study pharmacist will assign treatment sequentially according the sequence for each site.

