### *3.3.8.2.3 Therapist Selection, Training, Supervision, and Fidelity Monitoring*

It is important to specify the content of behavioral treatments in pharmacologic trials, and to ensure fidelity to the specified content. This is particularly important in studies of classic hallucinogens, since it is expected that the therapeutic benefits of the medication could be moderated by non-pharmacologic components of the treatment. We have adapted the procedures used in the COMBINE trial, streamlining them to some extent because the behavioral treatments are not being manipulated experimentally in the

current study, serving rather as the platform for the pharmacologic interventions. All sessions will be audio-recorded if possible. Checklists and rating forms for all components of the therapy will be developed based on those used in COMBINE. These will serve three purposes: to provide guidance to therapists in conducting sessions and allow them to document their self-assessed adherence; to provide material for supervision at the local level; and to provide material for formal fidelity monitoring, which will be done centrally at UNM.

**Therapist Qualifications.** Both the META and PSI therapists must have at least a master's degree in a related field or be pursuing a master's degree. At least one or both of the META and PSI therapists must be a licensed physician (MD) for all sessions.

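### Aim 4 bars site, the randomisation stratum, from the mediation model, so aligned site differences arising after baseline can bias the mediator-to-drinking path in either direction

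*Combined protocol and SAP*

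**What the plan says.** Section 3.3.12.5.2 (Aim 4) takes over the Aim 3 method: "Statistical procedures described for Aim 3 will be used to determine if the proposed mediators account for the effectiveness of the psilocybin administration". Mediator changes are taken at weeks 5 and 9, and heavy drinking at weeks 8 and 12. The section closes with an unconditional exclusion: "Performance site and the site by treatment group interaction terms will not be entered into the model".

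The borrowed method, in section 3.3.12.4.2, reads: "Tests of statistical mediation will use a product-of-coefficients approach with a bootstrapping procedure". The only covariate it names is baseline: "baseline values of the dependent variable will be entered in level 2". That section does not mention site.

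Site matters elsewhere in the plan:
- Section 3.3.5 makes it the stratum: "The randomization will be stratified by site and will consist of balanced varied size blocks within strata".
- The abstract gives the number: "Two to four sites will participate".
- For the primary outcome, section 3.3.12.3.2 starts with site in the model and drops it conditionally: "Site and the site-by-treatment interaction will be removed from the final model if not significant at the" 0.05 level.

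Section 3.3.12 refers to a statistical analysis plan for the full description. The text available for review contains no separate analysis of site for Aim 4.

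**The concern.** Mediation is inferred from the product of two coefficients. Path a is the effect of assigned drug on the change in craving, self-efficacy or readiness, and it is randomised. Path b is the association of that change with later heavy drinking given treatment, and it is observational. Anything that moves both variables and is left out of the model enters b.

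Site is a measured candidate for such a common cause. Recruitment plans are developed locally (3.3.6), and therapists are supervised locally (3.3.8.2.3). The plan also expects that "the therapeutic benefits of the medication could be moderated by non-pharmacologic components of the treatment". Suppose one site's participants show both a smaller fall in craving and more heavy drinking after dosing, for reasons tied to the site. A pooled b then counts that between-site contrast as evidence that craving carries the drug effect. Stratified randomisation balances arms within site but leaves this contrast in place.

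At stake is the answer to Hypothesis 4, which says that changes in these measures mediate the psilocybin effect. There is also an asymmetry. Site could be retained in the Aim 2 model for the treatment effect on heavy drinking, yet be barred from the model that explains that effect.

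**Working it through.** The plan gives no power, effect size or site variance for Aim 4, so there is no stated figure to reproduce.

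**Inputs.** From the documents: N = 180 × 0.95 = 171 (3.3.12.7), 2 to 4 sites, mediators as changes, and baseline drinking as covariate. Assumed: within-site SD of 1 for mediator change and drinking, within-site baseline-to-later-drinking correlation ρ = 0.5, true b = 0, one mediator-outcome pair per person, and the same site shift on both variables, with between-site variance v. Then ICC = v/(1 + v). For two sites, the gap between them is 2√v: 0.29, 0.46 and 0.67 SD at ICC 0.02, 0.05 and 0.10.

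**Worst case: none of the shift is present at baseline.** Without site in the model:
- bias in b = v/(1 + v) = ICC
- SE(b) = √[(1 − ρ² + ICC)(1 − ICC)/(N − 4)]
- rejection rate = Φ(z − 1.96) + Φ(−z − 1.96), with z = bias/SE

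| ICC | SE(b) | z | Rate by formula | Rate by simulation |
|---|---|---|---|---|
| 0.02 | √(0.77 × 0.98/167) = 0.0672 | 0.30 | 6.0% | about 6-7% |
| 0.05 | √(0.80 × 0.95/167) = 0.0675 | 0.74 | 11.5% | about 11-13% |
| 0.10 | √(0.85 × 0.90/167) = 0.0677 | 1.48 | 31.5% | about 31-34% |

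**Half of the shift present at baseline.** The change score then carries only half the shift, and baseline drinking absorbs part of the rest. At ICC 0.10, v = 0.111, and conditional on baseline drinking:
- cov(change, drinking) = v/2 − (v/4)(0.5 + v/2)/(1 + v/4) = 0.0556 − 0.0150 = 0.0405
- var(change) = 1.0278 − 0.0008 = 1.027
- bias in b = 0.0405/1.027 = 0.039, SE = 0.0687, z = 0.57, rate 8.9% (simulation about 9-10%)

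At ICC 0.05 the same steps give bias 0.019, z = 0.28 and a rate of 5.9% (simulation about 5-6%).

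**All of the shift present at baseline.** The change score removes it from the mediator, the bias in b is zero, and the rate is about nominal (5-6% by simulation).

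**Unaligned shifts.** If site effects on the two variables are unrelated but still wholly new after baseline, simulated rates are about 6-8% at ICC 0.05 and about 10% at ICC 0.10.

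**With site as a fixed effect.** The rate is about 3-6% in every scenario.

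**The product a×b.** A separate simulation tested the product itself with a Monte Carlo interval in place of the bootstrap (172 participants, path a = 0.5 SD, shift absent at baseline). Two sites 0.5 SD apart gave 12.3% false mediation without site and 3.9% with it. The mean b of 0.06 agrees with the formula: v = 0.5²/4 = 0.0625, and 0.0625/1.0625 = 0.059. At a gap of 0.3 SD the rate was 4.7%. Four sites spread over 0.5 SD gave 6.3%. With path a = 0, false mediation never exceeded 1.7%.

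**The case against.** The case for leaving the plan alone has real weight.

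- **The planned variables already remove stable site differences.** Mediators enter as changes, and baseline drinking is a covariate. A site that simply recruits people with higher craving and heavier drinking causes little trouble. If baseline for Aim 4 is weeks 1-4, as in Aim 2, it also covers early therapy sessions with the site's own therapists. This stands, and it is why the larger percentages are worst cases. It does not cover site differences that emerge after dosing.
- **Sites are standardised.** They share a manual, training, certification, central fidelity monitoring and eligibility criteria. This argues for small site effects. The sentence on non-pharmacologic components is about moderation of drug benefit and does not say that sites differ. No between-site variance is given to settle the matter.
- **The remedy is partial.** Severity, expectancy and other participant-level confounders of path b remain after site is entered. True, but that is no reason to exclude a known design factor.
- **Aim 4 is a mechanism analysis**, and the full SAP might contain a site-adjusted sensitivity analysis. The available text cannot settle this.

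A reader might go further and infer that rates of 11-34% are to be expected, that the error always favours finding mediation, that Aim 3 contains the same mistake, or that the lack of type I error protection for the three primary mediators enlarges this bias. The documents support none of these. The rates rest on assumed site effects. Opposing shifts can hide real mediation. The exclusion appears only under Aim 4, with Aim 3 silent on site. The multiplicity choice is separate and openly stated.

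**Conclusion.** The concern holds as a conditional weakness of Aim 4. Excluding the stratum leaves path b open to a bias that stratified randomisation cannot remove, and the plan gives no benefit to set against it. The size depends on three things that the documents do not supply: how much sites differ in mediator change, whether those differences line up with drinking, and how much was already present at baseline. Under the stated assumptions the excess is negligible at ICC 0.02 or when the shift is fully present at baseline. It is modest when half is present, and material only when aligned effects are largely new after baseline at an ICC of about 0.05 or more. A false mediation claim also needs psilocybin to move the mediator.

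The calculation uses one mediator-outcome pair per person, not the planned hierarchical model, so the rates are indicative. A reader might infer that the efficacy conclusion is compromised. It is not: the Aim 2 arm contrast is randomised and is analysed in a separate model.

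**What to change.** In section 3.3.12.5.2, replace the exclusion sentence with: *Site (the randomisation stratum) will be entered as a fixed effect in both the mediator and the drinking equations regardless of its p-value; the site-by-treatment interaction will not be entered.* The same specification can be used for Aim 3 for consistency; there it fills a silence and corrects no stated error.

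Cost: one sentence, no new data, and 1 degree of freedom with two sites or 3 with four, out of about 171 participants. In a simulation with no site differences and true b = 0.2, power fell from 84.2% to 83.5% (two sites) and from 84.3% to 83.7% (four sites). Any genuine between-site association of mediator and drinking will no longer contribute to b. Participant-level confounding of path b remains, and the report should say so.
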